### 3.3.5 Treatment Modifications for MLN9708-related AEs (Non-Hematologic Toxicities)

Treatment modifications due to MLN9708-related AEs are outlined in Table 3-3.

**Table 3-3 MLN9708 Treatment Modification (Delays, Reductions, and Discontinuations) Due to Adverse Events (Non-Hematologic Toxicities)**

Adverse Event (Severity)	Action on Study Drug	Further Considerations
Grade 1 peripheral neuropathy	
 
• No action
 
	Grade 1 signs and symptoms: asymptomatic; without pain or loss of function; clinical or diagnostic observations only[6]
New or worsening Grade 1 peripheral neuropathy with pain or Grade 2	
 
• Hold study drug until resolution to Grade <math>\leq</math> 1 or baseline
 
	Grade 2 signs and symptoms: Moderate symptoms; limiting instrumental activities of daily living (ADL)[6]
New or worsening Grade 2 peripheral neuropathy with pain or Grade 3	
 
• Hold study drug until resolution to Grade <math>\leq</math> 1 or baseline
 
• Reduce study drug to next lower dose upon recovery
 
	Grade 3 signs and symptoms: severe symptoms; limiting self-care ADL; assistive device indicated[6]
New or worsening Grade 4 peripheral neuropathy	
 
• Discontinue study drug
 
	
Grade 3 nonhematologic toxicity judged to be related to study drug	
 
• Hold study drug until resolution to Grade <math><</math> 1 or baseline
 
	Symptomatic recommendations noted in Section 3.4
If not recovered to <math><</math> Grade 1 or baseline within 4 weeks	
 
• Reduce study drug 1 to next lower dose upon return to <math><</math> Grade 1 or baseline
 
	
Subsequent recurrence Grade 3 that does not recover to <math><</math> Grade 1 or baseline within 4 weeks	
 
• Hold study drug until resolution to Grade <math><</math> 1 or baseline
 
• Reduce study drug to next lower dose
 
	Monitor closely, take appropriate medical precautions, and provide appropriate symptomatic care
Grade 4 nonhematologic toxicities judged to be related to study drug	
 
• Permanently discontinuing study drug
 
	

Once MLN9708 is reduced for any toxicity, the dose may not be re-escalated

### 3.3.5 Packaging and Labeling

#### **MLN9708**

For blistered material, the capsules are packaged in cold form foil-foil blisters with a paper backing for child-resistance.

MLN9708 is an anticancer drug and as with other potentially toxic compounds caution should be exercised when handling MLN9708 capsules.

The study drug MLN9708 capsules will be provided by Millennium. The study drug will be labeled and handled as open-label material, and packaging labels will fulfill all requirements specified by governing regulations. The formulation consists of 0.2-, 0.5-, and 2.0-mg capsules for oral administration.

MLN9708 capsules may be stored unopened at 2°C to 8°C (36°F-46°F). The capsules are individually packaged in cold form foil-foil blisters with a paper backing for child resistance. The capsules are in 1 × 4 blister strips that are individually perforated. The strips (1 × 4) are placed in cartons containing 6 strips (24 total capsules) of the same strength.

#### **Storage, Handling, and Accountability**

Upon receipt at the investigative site, MLN9708 should remain in the blister and carton provided until use or until drug is dispensed. The container should be stored at the investigative site refrigerated (36°F to 46°F, 2°C to 8°C). All excursions should be brought to Millennium's attention for assessment and authorization for continued use. Ensure that the drug is used before the retest expiry date provided by Millennium. Expiry extensions will be communicated accordingly with updated documentation to support the extended shelf life.

In countries where local regulations permit, MLN9708 capsules dispensed to the patient for take-home dosing should remain in the blister packaging and refrigerated as noted above until the point of use. The investigative site is responsible for providing the medication to the patient in the correct daily dose configurations. Comprehensive instructions should be provided to the patient in order to ensure compliance with dosing procedures. Patients who are receiving take-home medication should be given only 1 cycle of medication at a time. Patients should be instructed to store the medication refrigerated (36°F to 46°F, 2°C to 8°C) for the duration of each cycle. Patients should be instructed to return their empty blister

packs to the investigative site, rather than discarding them. Reconciliation will occur accordingly when the patient returns for their next cycle of take-home medication. Any extreme in temperature should be reported as an excursion and should be dealt with on a case-by-case basis.

Because MLN9708 is an investigational agent, it should be handled with due care. Patients should be instructed not to chew, break, or open capsules. In case of contact with broken capsules, raising dust should be avoided during the clean-up operation. The product may be harmful by inhalation, ingestion, or skin absorption. Gloves and protective clothing should be worn during cleanup and return of broken capsules and powder to minimize skin contact.

The area should be ventilated and the site washed with soap and water after material pick-up is complete. The material should be disposed of as hazardous medical waste in compliance with federal, state, and local regulations.

In case of contact with the powder (eg, from a broken capsule), skin should be washed immediately with soap and copious amounts of water for at least 15 minutes. In case of contact with the eyes, copious amounts of water should be used to flush the eyes for at least 15 minutes. Medical personnel should be notified. Patients are to be instructed on proper storage, accountability, and administration of MLN9708, including that MLN9708 is to be taken as intact capsules.

### **3.4 Management of Clinical Events**

#### Prophylaxis Against Risk of Infection

If lymphopenia is noted, patients may be at an increased risk of infection. In particular, lymphopenia can be associated with reactivation of herpes zoster and herpes simplex viruses. Antiviral therapy such as acyclovir or valacyclovir may be initiated as clinically indicated. Other antivirals are also acceptable.

#### Thromboembolism Prophylaxis

For patients at high risk, thromboprophylaxis according to ASCO guidelines or institutional standard of care is recommended.

#### Nausea and/or Vomiting

Standard anti-emetics, including 5-HT3 antagonists, are recommended for emesis occurring upon treatment initiation; prophylactic anti-emetics may also be considered.

Dexamethasone should not be administered as an anti-emetic. Fluid deficits should be corrected before initiation of study drug and during treatment.

### Diarrhea

Diarrhea should be managed according to clinical practice, including the administration of antidiarrheals once infectious causes are excluded. Fluid intake should be maintained to avoid dehydration. Fluid deficits should be corrected before initiation of treatment and during treatment.

### Erythematous Rash With or Without Pruritus

Rash has been reported with both lenalidomide and MLN9708. The lenalidomide-Induced rash is characterized as generalized, maculopapular, morbilliform, urticarial, papular, often with pruritus, and is noted as a warning/precaution in the lenalidomide package insert (PI). Serious skin reactions such as Stevens-Johnson Syndrome, toxic epidermal necrolysis, and erythema multiforme have been reported. Lenalidomide interruption

Or discontinuation should be considered as described in the PI/Summary of Product Characteristics (SmPC).

As with VELCADE, rash with or without pruritus has been reported with MLN9708, primarily at the higher doses tested. The rash may range from some erythematous areas to macular and/or small papular bumps that may or may not be pruritic over a few areas of the body or more generalized, or it may have been transient and resolved either spontaneously or with standard symptomatic measures such as oral or topical antihistamines. Prophylactic measures should also be considered if a patient develops a rash (eg, using a thick, alcohol-free emollient cream on dry areas of the body). In the case of rash, the use of a topical or oral steroid (eg, prednisone  $\leq$  10 mg per day or equivalent) is permitted.

**Thrombocytopenia**

Thrombocytopenia has been reported with both MLN9708 and lenalidomide. Blood counts should be monitored regularly as outlined in the protocol with additional testing obtained according to standard clinical practice. Thrombocytopenia may be severe but has been manageable with platelet transfusions according to standard clinical practice. MLN9708 or lenalidomide administration should be modified as noted as per dose modification recommendations when thrombocytopenia occurs. Therapy can be reinitiated at a reduced level upon recovery of platelet counts.

**Neutropenia**

Neutropenia has been reported with both MLN9708 and lenalidomide. Blood counts should be monitored regularly as outlined in the protocol with additional testing obtained according to standard clinical practice. Neutropenia may be severe but has been manageable with G-CSF according to standard clinical practice. MLN9708 or lenalidomide administration should be modified when neutropenia occurs, as noted in the dose modification recommendations in Table 3-2. Therapy can be reinitiated at a reduced level upon recovery of absolute neutrophil counts.

**Fluid Deficits**

Dehydration should be avoided because lenalidomide is substantially excreted by kidney, and MLN9708 may cause vomiting, diarrhea, and dehydration. Two cases of acute renal failure have been reported in patients treated at or above the MTD with IV administration of MLN9708. There has been no treatment-related renal failure reported in patients treated with PO MLN9708. Fluid deficits should be corrected before initiation of study drug and during treatment. Until further information is available, intake of NSAIDs while on this protocol should be avoided.

**Hypotension**

Symptomatic hypotension and orthostatic hypotension with or without syncope have been reported with ixazomib. Blood pressure should be closely monitored while the patient is on study treatment and fluid deficit should be corrected as needed, especially in the setting of concomitant symptoms such as nausea, vomiting, diarrhea, or anorexia. Patients taking medications and/or diuretics to manage their blood pressure (for either hypo- or hypertension) should be managed according to standard clinical practice, including

considerations for dose adjustments of their concomitant medications during the course of the trial. Fluid deficit should be corrected before initiation of study drug and as needed during treatment to avoid dehydration.

### **Posterior Reversible Encephalopathy Syndrome**

One case of posterior reversible encephalopathy syndrome, which ultimately resolved, has been reported with ixazomib. This condition is characterized by headache, seizures and visual loss, as well as abrupt increase in blood pressure. Diagnosis may be confirmed by magnetic resonance imaging (MRI). If the syndrome is diagnosed or suspected, symptom-directed treatment should be maintained until the condition is reversed by control of hypertension or other instigating factors.

### **Transverse Myelitis**

Transverse myelitis has also been reported with ixazomib. It is not known if ixazomib causes transverse myelitis; however, because it happened to a patient receiving ixazomib, the possibility that ixazomib may have contributed to transverse myelitis cannot be excluded.

## **3.5 Concomitant Treatment**

### **3.5.1 Permitted Concomitant Medications and Procedures**

All necessary supportive care consistent with optimal patient care shall be available to patients as necessary.

The following are examples of those permitted during the study:

- Growth factors (eg, granulocyte colony stimulating factor [G-CSF], granulocyte macrophage-colony stimulating factor [GM-CSF], recombinant erythropoietin).
- Patients may be transfused with red cells and platelets as clinically indicated.
- Prophylactic antibiotics for pneumocystis prophylaxis (such as Bactrim) is allowed.
- Antiviral therapy such as acyclovir is recommended for all patients.
- Concomitant treatment with bisphosphonates will be permitted.

- Patients who experience worsening neuropathy from baseline may be observed for recovery, and any supportive therapy or intervention may be initiated as appropriate at the discretion of the investigator. Dose reduction is suggested, when and if the patient resumes MLN9708 therapy.

### **3.5.2 Prohibited Concurrent Therapy**

The following medications and procedures are prohibited during the study.

Systemic treatment with any of the following metabolizing enzyme inhibitors is not permitted in this study A DDI with a strong inhibitor would increase MLN2238 exposure. (rationale: if there were to be a drug-drug interaction with an inhibitor, the MLN2238 exposure would be increased leading to a high probability of an adverse event):

- Strong inhibitors of CYP1A2: fluvoxamine, enoxacin, ciprofloxacin
- Strong inhibitors of CYP3A: clarithromycin, telithromycin, itraconazole, voriconazole, ketoconazole, nefazodone, and posaconazole

Systemic treatment with any of the following metabolizing enzyme inducers should be avoided, unless there is no appropriate alternative medication for the patient's use . A DDI with a strong inducer would decrease MLN2238 exposure Strong CYP3A inducers: rifampin, rifapentine, rifabutin, carbamazepine, phenytoin, and phenobarbital

The dietary supplements St John's wort and Ginkgo biloba are not permitted.

The following procedures are prohibited during the study:

- Any antineoplastic treatment with activity against MM except for drugs in this treatment regimen.
- Platelet transfusions to help patients meet eligibility criteria are not allowed within 3 days before study drug dosing.
- Adjuvant hormone therapy for breast or prostate cancer

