### **3. INVESTIGATIONAL PLAN**

#### **3.1 Overall Design and Plan of the Study**

Eligible patients will be enrolled and maintenance therapy on protocol no less than 60 days and must be initiated no more than 180 days post ASCT.

Patients will have standard restaging studies prior to initiation of therapy.

Standard post transplant therapy per institutional guidelines will be unaltered including prophylaxis therapy, vaccinations and restaging.

Patients who have completed ASCT and meet eligibility criteria will initiate maintenance therapy based on time on enrollment either in the phase dose escalation or expansion portion of trial.

Patients' clinical laboratory values and toxicity must be as specified below within 5 days before the first dose of study drug:

- Platelet count  $\geq 100,000/\text{mm}^3$
- Neutrophil count  $\geq 1000/\text{mm}^3$  (No growth factors within 5 days)
- Total bilirubin  $\leq 1.5 \times \text{ULN}$
- Alanine aminotransferase (ALT) and aspartate aminotransferase (AST)  $\leq 3 \times \text{ULN}$
- Creatinine  $< 2.5 \text{ mg/dL}$

Recovered (ie,  $\leq$  Grade 1 toxicity) from the reversible effects of autologous stem cell transplant.

Each cycle will be defined as a 28 day cycle. Drug holidays and break in therapy including those due to holidays, physician discretion and drug delivery are allowed as needed. Study drug will begin at Lenalidomide (10 mg/day); after three cycles , provided the ANC is  $\geq$  1000/ $\mu$ L, platelet count  $\geq$  100,000/ $\mu$ L, and all nonhematologic toxicity is  $\leq$  grade 1, then the dose may be increased to 15 mg/day at discretion of physician.

MLN 9708 will be dosed at 3 mg flat dose on days 1, 8, 15 administered orally.

Patients will be allowed to receive radiotherapy for palliation of symptoms during the course of maintenance therapy

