#### **3.2.1 Inclusion Criteria**

Each patient must meet all of the following inclusion criteria to be enrolled in the study:

1. Patient must have undergone autologous stem cell transplantation, with melphalan as a preparative regimen, within 12 months of initiation of induction therapy for newly diagnosed myeloma.
2. Time to initiation of maintenance therapy.

Patients may start maintenance therapy as early as 60 days post transplant and up to - 180 post transplant; as long as they meet the following criteria:

- Platelet count  $\geq$  100,000/mm^3
- Neutrophil count  $\geq$  1000/mm^3. (No growth factors within 5 days)
- Total bilirubin  $\leq$  1.5  $\times$  ULN
- Alanine aminotransferase (ALT) and aspartate aminotransferase (AST)  $\leq$  3  $\times$  ULN
- Creatinine  $<$  2.5 mg/dL
- Recovered (ie,  $\leq$  Grade 1 toxicity) from the reversible effects of autologous

3. Patients whose primary therapy was changed due to suboptimal response or toxicity will be eligible, however no more than 2 regimens will be allowed prior to ASCT.

4. Male or female patients 18 years or older.

5. Patients must have an Eastern Cooperative Oncology Group (ECOG) status of 0 to 2.

6. Voluntary written informed consent before performance of any study-related procedure not part of normal medical care, with the understanding that consent may be withdrawn by the subject at any time without prejudice to future medical care.

7. Female patients who:

- Are postmenopausal for at least 1 year before the Screening visit, OR
- Are surgically sterile, OR
- If they are of childbearing potential, agree to practice 2 effective methods of contraception, at the same time, from the time of signing the informed consent, during study treatment and for 28 days after the last dose of study treatment, OR agree to completely abstain from heterosexual intercourse

Male patients, even if surgically sterilized (ie, status postvasectomy), who:

- Agree to practice effective barrier contraception during the entire study treatment period and through 28 days after the last dose of study treatment, OR
- Agree to completely abstain from heterosexual intercourse

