## 3.2.2 Exclusion Criteria

Patients meeting any of the following exclusion criteria are not to be enrolled in the study:

1. Patient has  $\geq$  Grade 2 peripheral neuropathy.
2. Major surgery within 14 days before the first dose of study drug.

3. Radiotherapy within 14 days before enrollment
4. Known active central nervous system involvement
5. Systemic treatment, within 14 days before study enrollment, with strong inhibitors of CYP1A2 (fluvoxamine, enoxacin, ciprofloxacin), strong inhibitors of CYP3A (clarithromycin, telithromycin, itraconazole, voriconazole, ketoconazole, nefazodone, posaconazole) or strong CYP3A inducers (rifampin, rifapentine, rifabutin, carbamazepine, phenytoin, phenobarbital), or use of Ginkgo biloba or St. John's wort
6. Inability to swallow oral medication, inability or unwillingness to comply with the drug administration requirements, or GI procedure that could interfere with the oral absorption or tolerance of treatment.
7. Evidence of current uncontrolled cardiovascular conditions, including uncontrolled hypertension, uncontrolled cardiac arrhythmias, symptomatic congestive heart failure, unstable angina, or myocardial infarction within the past 6 months.
8. Female subject is pregnant or lactating.
9. Serious medical or psychiatric illness that could, in the investigator's opinion, potentially interfere with participation or completion of treatment according to this protocol.
10. QTc B > 470 milliseconds (msec) on a 12-lead ECG obtained during the Screening period. If a machine reading is above this value, the ECG should be reviewed by a qualified reader and confirmed on a subsequent ECG.
11. Ongoing or active systemic infection, known human immunodeficiency virus (HIV) positive, known active hepatitis B virus hepatitis, or known active hepatitis C virus hepatitis.
12. Infection requiring systemic antibiotic therapy or other serious infection within 14 days before study enrollment.
13. Known allergy to any of the study medications, their analogues, or excipients in the various formulations.

14. Participation in clinical trials with other investigational agents not included in this trial, within 21 days of the start of this trial and throughout the duration of this trial.
15. Failure to have fully recovered (ie,  $\leq$  Grade 1 toxicity) from the effects of prior chemotherapy regardless of the interval since last treatment.

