**Only enough lenalidomide for 1 cycle may be provided to the patient each cycle.**

If a dose of lenalidomide is missed, it should be taken as soon as possible on the same day. If it is missed for the entire day, it should not be made up.

Patients who take more than the prescribed dose of lenalidomide should be instructed to seek emergency medical care if needed and contact study staff immediately.

Accurate records will be kept in the source documents of all drug administration (including prescribing and dosing).

Research center personnel will review the dosing instructions with subjects. Subjects will be asked to maintain a diary to record the drug administration. Subjects will be asked to bring any unused drug and empty drug containers to the research center at their next visit. Research personnel will count and record the number of used and unused drug at each visit and reconcile with the patient diary.

MLN9708

All protocol-specific criteria for administration of study drug must be met and documented before drug administration. Patients should be monitored for toxicity, as necessary, and doses of MLN9708 should be modified as needed to accommodate patient tolerance to treatment; this may include symptomatic treatment, dose interruptions, and adjustments of MLN9708 dose (see Section 3.3.3) and per PI discretion.

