**3.3.3.1 Criteria for Beginning or Delaying a Subsequent Treatment Cycle**

Treatment with Lenalidomide and MLN9708 will use a cycle length of 28 days. For a new cycle of treatment to begin, the patient must meet the following criteria:

- ANC must be  $\geq$  1,000/mm^3.
- Platelet count must be  $\geq$  75,000/mm^3.

In addition, all other toxicity considered to be related to treatment with MLN9708 must have resolved to  $\leq$  Grade 1, to the patient's baseline values, or to a level considered acceptable by the physician (eg, hypokalemia that can be managed by replacements) before a new cycle of MLN 9708 treatment may begin.

If greater than  $> 4$  week delay in starting subusequent cycle due to recovery from toxicity, consider dose reduction in attributable drug.

If the patient fails to meet the above-cited criteria for initiation of the next cycle of treatment, dosing should be delayed until recovery. The maximum delay before treatment should be discontinued will be 6 weeks or at the discretion of the Principal Investigator.

Intracycle dosing :

Lenalidomide should be held if plt < **If platelet count  $\leq 30 \times 10^9/\text{L}$  or ANC  $\leq 0.75 \times 10^9/\text{L}$**   
**If platelet count  $\leq 30 \times 10^9/\text{L}$  or ANC  $\leq 0.75 \times 10^9/\text{L}$  until recovered to platelet > 75,000 and ANC > 1.0**

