## 8. APPENDICES

### 8.1 Study Flow Chart

Procedure	Screening ≤ 28 days from Initiation of therapy (may include Day 1)	Baseline	Cycle 1: (except cycle 1 day 1  ) 			all cycles beyond cycle 1		End of study	Follow up
			Cycle 1 Day 1 +/- 7 days	Day 8 +/-3 days (only dose escalation phase)	Day 15 +/-3 days ( only dose escalation phase)	Day 1 +/-7 days			
Informed consent	X								
Inclusion/Exclusion criteria	X								
Complete Medical Hx	X								
Confirmation Dx and status of disease and prior Rx	X								
MDASSI Questionnaire and Correlative Samples 		X					X 		
Record concurrent therapies/procedures	X								
Record adverse events	X	X					X	X	
Physical examination, vital signs Score 	X	X	X	X			X	X	
Skeletal survey( as clinically indicated)	X							X	
Bone Marrow aspiration and biopsy	X						X 	X	
12 Lead ECG	X								
Hematology 	X 	X	X	X			X	X	
Serum chemistry 	X 	X	X	X			X	X 	
TSH	x								
Ht, Wt, BSA	X	X					X	X	
Pregnancy test for females of child bearing potential	X	X 					X 	X	
Register Patient into Rev Assist® Program	X								
Serum and urine M component quantification	X						X (every 1-3 cycles)	X	
24hour urine for protein measurement	X						X (every 1-3 cycles)	X	
Prescribe lenalidomide via RevAssist®		X					X		
Serum for FreeLite Testing	x						X (every 1-3 cycles)	X	
Dispense study drug for next cycle		X					X		
Perform drug accountability			X				X	X	
Survival status									X 

1. A repeat bone marrow biopsy will only be done at time of suspected complete remission to document complete remission per standard clinical practice and at physician discretion.
2. To include Na, K, Cl, Co2, Ca, Mg, Phosphorous, BUN, Cr., glucose, albumin, alk phos, total Bili, ast/alt.
3. WBC, differential, Hgb, Hct and platelet count
4. Screening CBC and Chemistry parameters need to meet criteria to initiate dosing in section 3.1 within 5 days of starting protocol directed therapy.
5. Pregnancy testing will be done 10-14 days prior to starting therapy and within 24 hours prior of starting lenalidomide on day 1
6. These will be done every 1-3 cycles.

**7. DAY 8 AND DAY 15 (+/- 3 DAYS ASSESSMENTS ARE TO BE DONE DURING CYCLE 1 AND DURING THE CYCLE THE PHYSICIAN DOSE ESCALATES**

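### Minor: the platelet-transfusion ban looks back 3 days from dosing, but the qualifying count may be up to 5 days old, so it can be transfusion-supported within the rules

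*Combined protocol and SAP*

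**What the plan says.** The ban is in section 3.5.2: "Platelet transfusions to help patients meet eligibility criteria are not allowed within 3 days before study drug dosing".

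The count it protects is governed by section 3.1, where the laboratory values, including platelets of at least 100,000/mm3, "must be as specified below within 5 days before the first dose of study drug". Footnote 4 of the flow chart (section 8.1) gives the same window: "Screening CBC and Chemistry parameters need to meet criteria to initiate dosing in section 3.1 within 5 days of starting protocol directed therapy".

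The platelet line in sections 3.1 and 3.2.1 has a threshold and nothing more. The neutrophil line beside it adds "No growth factors within 5 days", without saying from which date those 5 days are counted.

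Two recovery criteria also apply at entry. Section 3.1 asks for toxicity of Grade 1 or less "from the reversible effects of autologous stem cell transplant". Item 15 of section 3.2.2 excludes patients who have not recovered to that grade "from the effects of prior chemotherapy regardless of the interval since last treatment".

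**The concern.** The ban exists so that a patient does not enter on a platelet count raised by transfusion. To do that, it has to control the time between the transfusion and the blood draw. As written, it controls the time between the transfusion and the first dose. Because the draw may come up to 5 days before dosing, the two earliest draw days lie inside the laboratory window and outside the ban.

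What is at stake is an entry safety check. Section 3.4 names thrombocytopenia as a reported effect of both study drugs and says that it may be severe. A site following the text exactly could start both drugs on a supported count and record no deviation.

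**Working it through.** **Inputs.** Laboratory window: 5 days before the first dose (section 3.1; footnote 4). Ban: 3 days before dosing (section 3.5.2). Set the first dose as day 0. The plan gives no figure of its own to reproduce.

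**Step 1, counting in calendar days.** Permitted draw days run from -5 to 0. The ban covers day -3 onward, so the last permitted transfusion day is -4. A transfusion can raise a count only if it comes no later than the draw, so

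shortest permitted gap = draw day - min(draw day, -4).

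**Step 2, counting in hours.** For a draw h hours before dosing, shortest permitted gap = max(0, 72 - h).

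| Draw day | Calendar-day gap | h | Hour gap |
|---|---|---|---|
| -5 | -5 - (-5) = 0 days | 120 | 0 h |
| -4 | -4 - (-4) = 0 days | 96 | 0 h |
| -3 | -3 - (-4) = 1 day | 72 | 0 h |
| -2 | -2 - (-4) = 2 days | 48 | 24 h |
| -1 | -1 - (-4) = 3 days | 24 | 48 h |
| 0 | 0 - (-4) = 4 days | 0 | 72 h |

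Both readings give zero on days -5 and -4. They differ on the later days, so the conclusion uses only what they share: no secured gap on the two earliest days, and a gap that grows from short as the draw approaches dosing.

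**Step 3, whether another rule closes the gap.**

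- Section 3.3.2, on giving MLN9708: "All protocol-specific criteria for administration of study drug must be met and documented before drug administration". A passing count from day -5 meets this; it does not ask for a new one.
- The flow chart lists hematology after screening, around Cycle 1 Day 1 (+/- 7 days). Footnote 4 ties the section 3.1 thresholds to the screening sample, and the later sample has no threshold.
- The 75,000/mm3 requirement is in section 3.3.3.1, headed "Criteria for Beginning or Delaying a Subsequent Treatment Cycle". It concerns later cycles and has no transfusion condition.
- The MLN9708 hold in Table 3-2, at 30 x 10^9/L or below, excludes Day 1. The lenalidomide hold in section 3.3.3.1 uses the same level with no such exclusion, but 30 x 10^9/L is 30,000/mm3, far below the 100,000/mm3 entry level.
- The Grade 1 recovery criteria do not mention transfusion.

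None of these requires an untransfused or rechecked count of 100,000/mm3 before the first dose.

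**Step 4, whether a longer ban would be enough.** With a 5-day ban before dosing, the last permitted transfusion is day -6, and a day -5 draw has a gap of -5 - (-6) = 1 day. Lengthening the ban still leaves a supported count possible. Tying it to the draw, on the same calendar convention, puts the last permitted transfusion at draw day - 4. The gap is then 4 days on every draw day, or 72 hours on the hour reading.

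**The case against.** The strongest reply is that this hardly matters. Patients start 60 to 180 days after transplant and must have recovered to Grade 1. One who needs platelets to reach 100,000/mm3 would be hard to call recovered, whichever day the blood is drawn. Toxicity is evaluated before each cycle. Footnote 7 adds Day 8 and Day 15 assessments in Cycle 1, although the column headers limit them to the dose escalation phase. The platelet holds apply after that. This stands, and it is why the point is minor. It does not close the gap, because none of these provisions asks whether the qualifying count was supported.

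A second reply is that the purpose of the ban is plain and sites will apply it sensibly. That is likely, but the text limits the bar to 3 days before dosing.

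A third reply is that the plan sets no interval between transfusion and count, so 3 days is not its own standard for that interval. This is correct. A reader might infer from the table that most draw days fail the plan's requirement. The documents do not support that: the 3 days in section 3.5.2 run to dosing, and the number of days that look short depends on how days are counted.

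**Conclusion.** The two windows do not line up, and no other provision makes up the difference. A count drawn on day -5 or -4 can follow a same-day platelet transfusion without breaching either rule. This rests on the wording of the two rules alone and holds on both the day and the hour reading.

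The size is minor. The documents give no transfusion rate and no size or duration of a transfusion rise, so the number of patients affected cannot be estimated; it is probably no more than an occasional one. The table describes calendar rules, not shares of patients.

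A reader might also infer that early toxicity counts, and so the stopping rule, are compromised. The documents give nothing to support that. The toxicity boundaries and Tables 1 to 3 in section 5 do not depend on the entry platelet count, and no operating characteristic changes.

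**What to change.** State in sections 3.2.1 and 3.5.2 that no platelet transfusion may be given within 3 days before the qualifying platelet count, and word section 3.1 and flow-chart footnote 4 to match. The 3 days is carried over from the existing rule. Say whether it means 72 hours or calendar days. Keep the present ban on eligibility transfusions within 3 days before dosing.

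Do not extend the new rule to transfusions given for other clinical reasons after an unsupported qualifying count. Take a patient who qualifies unsupported on day -4 and is transfused for another reason on day -2. A mandatory repeat count would wait until day -2 + 3 = +1 in hours, or -2 + 4 = +2 in calendar days. That is a delay of 1 to 2 days with no gain in the validity of the count already drawn.

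The cost is one sentence with matching edits in four places. A patient transfused on day 0 to reach eligibility can first be dosed on calendar day 4 under either rule, provided that under the new rule the day 4 count passes and is reported the same day. A patient transfused for another reason before the count, who need not wait today, would wait 72 hours or 4 calendar days from the transfusion for the count. In practice this means an occasional repeat blood count or a short start delay.
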